SPECIFIC AIM #1: To determine if anti-inflammatory treatment with etanercept or alpha-1 antitrypsin during the critical peri-transplant engraftment period improves islet engraftment and function after islet autotransplant, as assessed by area under the curve for C-peptide on mixed meal tolerance testing (oral stimuli), acute insulin response to glucose-potentiated arginine stimulation (IV stimuli), and insulin requirements at day 90 post-transplant. The primary endpoint of the maximally stimulated acute insulin response to arginine (AIRmax) from GPAIS at day 90 will allow us to rapidly identify the most promising therapeutic agent for further development and testing in a large randomized trial.

SPECIFIC AIM #2: To gather pilot data on the long-term impact of etanercept or alpha-1 antitrypsin administered during the peri-transplant period by evaluating islet function at 1 and 2 years post-transplant, as assessed by area under the curve for C-peptide on mixed meal tolerance testing (oral stimuli), acute insulin response to glucose-potentiated arginine stimulation (IV stimuli), and insulin requirements (units/kg/day) at 1 year post-TPIAT. In addition, insulin requirements and fasting/stimulated C-peptide by MMTT will be assessed at yearly intervals from year 3-5 post-transplant.

SPECIFIC AIM #3: To evaluate the mechanistic effects of etanercept and alpha-1 antitrypsin on inflammation, islet cell viability/survival, and beta cell apoptosis. This will be assessed by circulating cytokine and chemokine levels and measurement of circulating unmethylated DNA (a recently validated marker of beta cell death in T1DM) in patient serum.

The **goal** of the current research is to select the anti-inflammatory agent with the greatest potential to preserve islet mass early after TPIAT.

[figure not shown]
STUDY DESIGN OVERVIEW

Overview of Clinical Trial Design for All Aims

In this randomized, controlled non-masked trial, 45 patients age 18-65 years with chronic pancreatitis who are accepted for TPIAT procedure based on standard clinical criteria will be enrolled and randomized 1:1:1 to three study arms:

- 1) Alpha-1 antitrypsin (A1AT), 90 mg/kg/week IV, administered days -1, and +3, 7, 14, 21, and 28.
- 2) Etanercept administered as 50 mg SQ prior to the islet infusion (day 0) and 25 mg SQ on days 3, 7, 10, 14, 21 post-transplant.
- 3) Standard TPIAT care

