Patients will be seen in follow up at 90 days and 1 year post-transplant for metabolic testing. The maximally stimulated acute insulin response (AIRmax) obtained from glucose potentiated arginine-induced insulin secretion (GPAIS) at 90 days post-transplant is the primary endpoint for the study. AIRmax has previously been demonstrated to correlate best with islet mass in human and animal models; by assessing AIRmax at 90 days post-transplant, we will be able to rapidly evaluate the therapeutic impact of these agents and select the agent most promising for further study and development. Mechanistic studies will be performed frequently throughout the early transplant period. Inflammatory cytokines will be measured by repeated serum sampling in the first 1 week post-transplant. Unmethylated insulin DNA levels will be monitored in the first 1 month post-transplant. Insulin requirements and fingerstick blood glucoses will be monitored throughout the study duration. Key secondary endpoints include the area under the curve (AUC) for C-peptide from mixed meal tolerance testing, the acute insulin response (AIRglu) on IV glucose tolerance test, the acute C-peptide response to glucose (ACRglu) on IVGTT, and the maximally stimulated C-peptide response (ACRmax) from GPAIS at day 90 and 1 and 2 years, and the AIRmax at 1 and 2 years, as well as average daily insulin requirements at each time point. As an exploratory component, we will continue to collect the basic clinically available measures of insulin use/dose, HbA1c, and simple fasting and stimulated glucose and C-peptide from a mixed meal test annually for years 3-5 post-transplant, all part of the patients' routine cares.

Study Treatment

Study drugs: The two investigational agents administered in this study are as follows:

- 1) Alpha-1 antitrypsin (Aralast NP) intravenously at a dose of 90 mg/kg IV weekly. Treatment will be started 1 day prior to surgery and on days +3, 7, 14, 21, and 28 after infusion. This is infused as a rate of no more than 0.2 mL/kg body weight/minute, and may be slowed depending on patient tolerability.
- 2) Etanercept: dosing in adult recipients is 50 mg SQ on day 0, and 25 mg SQ on days 3, 7, 10, 14, 21.

All medication doses will be administered in the hospital (during post-operative hospitalization) or in the research center by an RN.

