A local follow up with telephone or face-to-face encounter to review insulin requirements, blood glucose logs, and obtain local mixed meal tolerance test results (part of standard clinical care) will occur at years 3, 4, and 5 (all \pm 2 months) for exploratory data on long-term efficacy. This information will be readily available, as it is part of the standard routine care of all TPIAT recipients at UM.

Subject screening visit

Subjects’ medical history will be reviewed from the electronic medical record and from history obtained from the patient to confirm eligibility. In addition, the following screening assessments will be performed at a screening visit within 4 weeks prior to the scheduled surgery date, after informed consent has been obtained:

- Complete metabolic battery (includes hepatic panel, creatinine, fasting glucose)
- CBC with differential and platelets
- Urine pregnancy test in women with child-bearing potential (if \geq 7 days since screen, repeat prior to first dose of study drug administration; UPT not necessary in females s/p hysterectomy procedure)
- Hepatitis C and hepatitis B serology, HIV ELISA
- IgA level
- Mantoux skin test or Quantiferon (serum) for TB screening
- Hemoglobin A1c level
- Mixed Meal Tolerance Test
- IV glucose tolerance test
- Glucose potentiated arginine-induced insulin secretion

Table. Study Flowchart (year 0-2)

	screening	Days 0-7	Days 7, 14, 21, 28	Day 60	Day 90	Day 365 (Year 1)	Day 730 (Year 2)
Study Visit Assessments (abbreviated)							
Insulin Use/Dose (u/kg/day, endpoint)			X		X	X	X
Mixed Meal Tolerance Test (AUC C-)	X				X	X	X
IVGTT (AIRglu, ACRglu)	X				X	X	X
GPAIS (AIRmax, ACRmax)	X				X	X	X
HbA1c level	X				X	X	X
iPro2 (6 day CGM)					X	X	X
Complete metabolic panel, CBC	X		X*		X	X	X
Random morning C-peptide and glucose			Day 7, 14				
Fasting glucose, C-peptide, creatinine	X		Day 28		X	X	X
Drug safety assessments (PE, hx, labs)		X	X				
Inflammatory cytokines (see text)**		X					
Unmethylated insulin DNA levels**		X	X				
Safety assessment (phone visit for symptoms)				X			
Islet Assessments (see text)		Day 0					

* **Years 3, 4, and 5:** Telephone or face-to-face review of insulin use/dose; labs (HbA1c, clinical MMTT)

** Drawn at multiple time points, as detailed in the methods for Specific Aim #3.

Design and Methods to Evaluate Specific Aim #1

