In addition to the metabolic data collected under this protocol, all TPIAT patients are enrolled in a prospective follow up study tracking diabetes, pain, and health related quality of life outcomes on an ongoing basis. Under this protocol, patients complete the SF-36 health related quality of life instrument and institutional derived questionnaires that include self-report of daily insulin use, pain symptoms, and pain medications. These instruments are administered at 3 months and 6 months after TPIAT and then once yearly after TPAIT. Copies of these instruments are included in the supplementary materials for reference. These assessments will permit long-term follow up of the study participants for both insulin requirements and health-related quality of life outcomes.

Design and Methods to Evaluate Specific Aim #3

SPECIFIC AIM #3: To evaluate the mechanistic effects of etanercept or alpha-1 antitrypsin on inflammation, islet cell viability/survival, and beta cell apoptosis. This will be assessed by repeated measurement of circulating cytokine and chemokine levels and circulating unmethylated DNA (a recently validated marker of beta cell death in T1DM) in patient serum during days 0 - 28.

Hypothesis 1: Peak levels and area under the curve for inflammatory cytokines will be lower in recipients treated with alpha-1 antitrypsin and etanercept.

Hypothesis 2: Lower rates of beta cell death will be observed post-transplant in the A1AT-treated and etanercept-treated groups, compared to standard of care, as evidenced by lower levels of circulating unmethylated insulin DNA in the patient serum.

To evaluate the potential mechanistic effects of the two drug therapies, we will obtain frequent serum measurements in recipients for critical markers including key cytokines/chemokines and markers of coagulation (the instant blood mediated inflammatory reaction), and markers of circulating exocrine tissue (trypsinogen). In addition, we will profile in each patient beta cell death(islet loss) using the novel marker for unmethylated insulin DNA. Unmethylated insulin DNA is specific to beta cells, and elevated levels in serum indicate beta cell death. Patient assessments are described in detail below.

1) Patient assessments:

- a. **Inflammatory Cytokines:** Patient serum will be assayed for TNF α , IL-1, IL-6, IL-8, IL-10, MCP-1, IP-10, and CCL2—at pre-surgical (x2 draws) and pre-infusion baseline, and at times 1, 3, 6, 12, 24,

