and 72 hours and 7 days after islet infusion. Assays will be performed using a Luminex ® multiplex bead cytokine kit. These measures were selected based on the literature suggesting relative importance in islet transplantation. These assessments are run in a CLIA certified cytokine laboratory (University of Minnesota cytokine laboratory).

In addition, thrombin-antithrombin complexes, C3a, and C-peptide will be obtained pre-infusion and at times 1, 3, and 24 hours post-transplant, as a marker of the instant blood mediated inflammatory response.

- b. Unmethylated insulin DNA: This novel marker has recently been validated as a measure of beta cell loss in new onset type 1 diabetes. Dying beta cells release unmethylated insulin DNA into the serum (43). The assay technique is performed as described by Herold et al (43). DNA is purified from 200 microliters of serum, using QIAamp DNA blood kits, and bisulfite treated using EZ DNA methylation kit. Unmethylated insulin DNA is measured by real-time PCR. Levels are elevated preoperatively and in new onset T1DM, but lowered when T1DM subjects are treated with teplizumab to preserve beta cell mass. Thus, we propose that this novel marker will provide critical mechanistic data on post-transplant loss of beta cell mass. This marker will be drawn prior to surgery and infusion (x 2 samples) and at 15 min, 30 min, 1, 3, 6, 12, 24, 72 hours, and 7, 14, and 28 days post-transplant, and repeated at each follow up visit (90 day, 1 year, 2 year).
- c. Alpha-1 antitrypsin levels: Measured at pre-treatment and prior to each infusion in the A1AT-treated group. In the control and etanercept groups, these levels will be measured at baseline and weekly through day 28 for comparison.
- d. Trypsin and Trypsinogen activated peptide (TAP): To determine if dying acinar cells release activated proteases which degrade the insulin molecules in systemic circulation, trypsin levels will be measured in the patient's serum pre- and at 12 and 24 hours post-islet infusion and by detection of TAP in the urine at 24 hours post-transplant by enzyme immunoassay (81). TAP is a small, measureable peptide that is released when trypsinogen is activated to trypsin.

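### No cytokine or insulin-DNA sample is required before the first A1AT dose, so as scheduled the baseline for these two markers is post-dose in the A1AT arm and untreated in controls

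*Combined protocol and SAP*

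**What the plan says.** **Dosing.** Under Study Treatment, A1AT is timed as follows: "Treatment will be started 1 day prior to surgery and on days +3, 7, 14, 21, and 28 after infusion". The design overview gives the second active arm as "Etanercept administered as 50 mg SQ prior to the islet infusion (day 0" and later days.

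**Aim 3 text.** Cytokines are to be drawn "at pre-surgical (x2 draws) and pre-infusion baseline, and at times 1, 3, 6, 12, 24" hours and later. For insulin DNA, item b says "This marker will be drawn prior to surgery and infusion (x 2 samples", followed by post-infusion times. Neither item gives the pre-surgical draws a day, or says whether they come before or after the first dose. The statement of Aim 3 in the same section puts the repeated measurements "in patient serum during days 0 - 28". Item b also says of insulin DNA: "Levels are elevated preoperatively and in new onset T1DM".

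**Schedules.** In the Study Flowchart (year 0-2), the rows "Inflammatory cytokines (see text" and "Unmethylated insulin DNA levels" are blank at screening and first marked in the column for days 0 to 7. In the detailed visit schedule before the reference list, both markers are first marked at the transplant visit. The screening column and the column for day -1 or 0 are blank. The A1AT dose is entered in that day -1 or 0 column.

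**Analysis.** The data analysis section compares post-transplant peak and AUC in a linear model that adjusts for islet mass and BMI stratum, and adds a random-intercept mixed model for the repeated values. No baseline marker value is a covariate in either.

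**The concern.** A baseline is useful only if it means the same thing in every arm. Here the samples carrying that name would follow one dose of drug in the A1AT arm, precede all treatment in controls, and fall on an unstated side of the first dose in the etanercept arm.

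This bears on interpretation because the protocol itself expects insulin DNA to be raised before surgery, so patients will differ at the start. With about 15 per arm a chance imbalance is plausible, and a post-dose value cannot reveal it. The Objectives section says the early mechanistic data will help decide which agent goes forward. A pre-dose sample that was not taken cannot be recovered later.

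**Working it through.** The plan states no figure on this point. The check sets the schedule rows beside the dosing rows, then follows the consequence through the planned and unplanned analyses.

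**1. First scheduled draw against first dose**

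| Item | Flowchart | Detailed schedule | Aim 3 text |
|---|---|---|---|
| Cytokines | Days 0-7 only | Transplant visit, days 3 and 7 | Two pre-surgical draws (undated), one pre-infusion, then post-infusion |
| Insulin DNA | Days 0-7, then days 7 to 28 | Transplant visit, days 3 to 28, 90, 365, 730 | Two samples before surgery and infusion (undated), then post-infusion |
| A1AT level | Not listed | Screening, day -1 or 0, days 7 to 28 | Explicit pre-treatment sample |
| A1AT dose | Not listed | Day -1, days 3 to 28 | Not applicable |

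Cytokine or insulin-DNA draws marked before day 0 or the transplant visit: none in either schedule. Draws that the text places before the first A1AT dose: none. The A1AT level row shows that a pre-dose sample was scheduled where one was intended.

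**2. By arm.** The detailed schedule requires the day -1 or 0 visit only for the two drug arms. Screening is therefore the only marked visit before the transplant visit that all three arms share, and it is blank for both markers.

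**3. Effect on each kind of analysis.** Let the untreated baseline average B. Let the first A1AT dose lower the marker by d before the draw, and let full treatment lower the post-transplant value from Y to Y - t. The documents do not give d.

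- Planned contrast, post-transplant only: (Y - t) - Y = -t. It does not involve d.
- Change from baseline: [(Y - t) - (B - d)] - [Y - B] = -t + d. The apparent benefit shrinks by d.
- Adjustment for the post-dose baseline with slope b: -t - b × (-d) = -t + b × d. This is also distorted, unless b or d is zero.
- Mixed model: the data analysis section does not say whether pre-infusion values enter the series. Its listed fixed effects include treatment but no time term. Any pre-infusion values that enter would be averaged into the treatment effect, and they mean different things in each arm.

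**4. Possible gain from a true baseline.** Adjusting for a covariate with correlation r removes a share r² of the residual variance. The range of r is an assumption, since the documents give none.

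- r = 0.3: 0.3² = 9%.
- r = 0.7: 0.7² = 49%.

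For scale, the plan's detectable difference of 1.06 SD at 15 per group and 80% power reproduces as 1.0598 with a two-sided 5% t-test. Multiplying by √(1 - r²) gives 1.06 × √0.91 = 1.01 SD and 1.06 × √0.51 = 0.76 SD.

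**The case against.** Two stronger readings are tempting, and the documents support neither.

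A reader might infer that the A1AT arm definitely has no drug-free sample. The flowchart is labelled abbreviated and has no day -1 column, so it could not show a draw on that day. Both schedules refer to the text for exact times, and the text lists the pre-surgical cytokine draws separately from the pre-infusion one. A site could take them before the day -1 dose. This much stands: the absence of a drug-free sample is not established. But the footnote in the detailed schedule concerns the several draws within the transplant visit and adds no earlier visit. The day 0 to 28 window in the Aim 3 statement points the same way. Nothing requires an earlier sample.

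A reader might also infer that the Aim 3 results are biased. The planned comparisons use post-transplant values, and under randomization these are valid without any baseline. No change-from-baseline contrast is planned. That stands too, so the distortion in step 3 applies only to analyses outside the plan or left open by it.

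Two further points are fair. The problem does not extend to every Aim 3 measure, since A1AT levels have a pre-treatment sample. And a sample taken up to 4 weeks before surgery may correlate only weakly with perioperative peaks.

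**Conclusion.** The concern holds in a limited form. The protocol requires no cytokine or insulin-DNA sample before the day -1 A1AT dose. Followed as scheduled, one third of the planned patients (15 of 45) would have a post-dose value under the name baseline, against an untreated value in controls. For etanercept the order of the pre-infusion draw and the dose needs to be stated.

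The planned peak and AUC comparisons remain valid. What is lost is the baseline-comparability check and a covariate free of treatment effect, and the protocol leaves open whether pre-infusion values enter the AUC or the mixed model.

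The conclusion rests on reading the transplant visit as day 0 or later, which follows from its place after the day -1 or 0 column. It also assumes that no protocol text outside that available for review dates these draws. The size of d and the correlation r are unknown, so neither a bias nor a precision gain can be quantified from the documents. This is a secondary-aim matter, worth correcting because the edit is small and the sample cannot be obtained afterwards.

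**What to change.** Reconcile the flowchart, Aim 3 items a and b, and the detailed schedule so that one sample of each marker is drawn before any study drug in every arm:

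- Mark cytokines and insulin DNA at screening, where all three arms already give blood. For cytokines, move one of the two pre-surgical draws there.
- The insulin-DNA wording may mean one sample before surgery and one before infusion. Either move the pre-surgical one and keep the pre-infusion one, or add a small aliquot (the assay uses 200 microliters of serum).
- Call only the screening sample baseline. Label the day 0 draws pre-infusion, and state their order relative to the first dose in each arm.
- Add the baseline value as a covariate in the Aim 3 peak, AUC and mixed models. State that pre-infusion values stay out of the post-transplant AUC and the longitudinal outcome series.

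The cost is a schedule edit and a few sentences in the analysis section, with no extra cytokine assay and at most one extra insulin-DNA assay per patient. No dose or dosing time changes. The downside is a baseline that may be up to 4 weeks before surgery, though the travel section allows screening in the week before surgery. The precision gain may be small if the correlation is low.

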In order to adequately assess the impact of any therapy on islet engraftment, it is important to have endpoints that reflect islet mass. Because it is not possible to directly quantify the number of islets that engraft and survive in the liver post-transplant, we have carefully selected surrogate endpoints that reflect beta cell function and mass. We will assess several previously validated measures: 1) C-peptide response to a mixed meal tolerance test (MMTT), 2) the acute C-peptide and insulin response to intravenous glucose tolerance (IVGTT), and glucose potentiated arginine-induced insulin secretion (GPAIS).

The oral stimulus used most often in the TPIAT setting and in trials of new onset type 1 diabetes mellitus is the mixed meal tolerance test, in which the subject ingests a standard amount of Boost High Protein or a similar beverage. The MMTT is an accepted measure of beta cell *function* in islet transplant and diabetes studies (7, 71, 72), and it is simple to perform in the clinic setting. However, it may be less useful than the intravenous stimuli as a direct measure of islet *mass* (73). Intravenous stimuli—dextrose and/or arginine—have been shown to correlate with islet mass in animal and clinical transplant models (74-76). Both the acute insulin response to glucose (AIRglu) derived from the IVGTT and the maximal acute insulin response to arginine (AIRmax) measured from GPAIS correlate strongly with transplanted islet mass in patients who maintain euglycemia long-term (74). While transplanted islet mass is not the same as engrafted islet mass, these studies were performed in patients who were specially selected from those with optimal long-term beta cell function, and so were likely the recipients with the best engraftment. Thus, they appear to be reasonable surrogate measure for engrafted beta cell mass. Both measures were superior to a simple arginine stimulation test (22). In allotransplant patients, the AIRglu and AIRmax at 3 months post-transplant predicted insulin independence at 1 year. Thus, this test performed early after transplant was predictive of key long-term clinical outcomes (22).

Measures of islet loss

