This is a pilot, parallel-arm study to compare etanercept, A1AT, and control groups; the primary outcome is maximal potentiated arginine induced insulin secretion (AIRmax) measured at 90 days posttransplant. We propose to enroll 15 patients in each group which will give 80% power to detect a difference between any two groups of at least 1.06*(within-group standard deviation of the outcome). From preliminary data for AIRmax measured more than one year post-transplant, the study will have 80% power to detect a difference of at least 33 mU/mL in pairwise comparisons of AIRmax between each of the 3 groups, corresponding to a 24% increase over standard treatment (control group).

The table below shows estimated minimum detectable differences for main outcomes, based on means and standard deviations from preliminary testing performed at 1 year post-transplant (for IVGTT and MMTT) or beyond 1 year post transplant (GPIAS) in this population of TPIAT recipients.

Test	Derived Measure	minimum detectable difference	n	Mean	SD
GPAIS	AIRmax (mU/mL)	33	10	137	31
IVGTT	AIRglu (mU/mL*min)	162	33	169	153
	ACRglu (ng/mL *min)	8.8	36	9.8	8.3
MMTT	AUC C-peptide (ng/mL *min)	147	39	295	139
	AUC glucose (mg/dL *min)	3790	39	16,037	3,579

For specific aim 1, the primary outcome, AIRmax, and other measurements at day 90 will be compared between treatment groups with a linear model to adjust for transplanted islet mass and the randomization stratum, BMI (< or \geq 27 kg/m²). For aim 2, the same analysis will be performed for measurements made at 1 year and 2 years post-transplant. In addition, we will assess whether day 90 AIRmax and AIRglu measurements predict insulin independence at 1 and 2 years post-transplant using a logistic regression model. For aim 3, repeated measurements during the weeks immediately post-transplant will be summarized by peak and area under the curve for comparison by the same linear model used for aim 1, i.e., adjusting for transplanted islet mass and the randomization stratum. We will also compare the groups based on the longitudinal series of measurements using a mixed-effects linear model with fixed effects of treatment group, transplanted islet mass and randomization stratum, and a random intercept for each participant to model the correlation between repeated measurements from the same person.

POTENTIAL RISKS AND BENEFITS

Forseeable Risks

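### Is the stated 80% power for a 24% gain in day-90 AIRmax unsafe because its SD is much smaller, relative to the mean, than those of the other insulin and C-peptide measures?

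*Combined protocol and SAP*

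**What the plan says.** Under Sample Size and Plan for Data Analysis, the protocol calls the trial a pilot. It first expresses power in SD units: 15 patients per group give 80% power for a difference of 1.06 within-group SDs between any two arms. It then converts this for the primary endpoint: "the study will have 80% power to detect a difference of at least 33 mU/mL in pairwise comparisons of AIRmax". It puts the relative size of that gain at 24% above the control arm, and names the source of the SD as later follow-up data: "From preliminary data for AIRmax measured more than one year post-transplant".

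The table beneath prints n = 10, mean 137 and SD 31 for AIRmax, and states that these data come from testing "beyond 1 year post transplant (GPIAS) in this population of TPIAT recipients". It also gives AIRglu (n = 33, mean 169, SD 153), ACRglu (n = 36, mean 9.8, SD 8.3), AUC C-peptide (n = 39, mean 295, SD 139) and AUC glucose (n = 39, mean 16,037, SD 3,579), all measured at one year. No day-90 SD is given, and neither alpha nor sidedness is stated.

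The arms will be compared "with a linear model to adjust for transplanted islet mass and the randomization stratum, BMI".

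**The concern.** AIRmax is the primary endpoint, yet its planning SD rests on the smallest sample in the table and is 2 to 4 times smaller, relative to its mean, than those of the other insulin and C-peptide measures. AIRglu and AIRmax come from the same morning's testing, and the background section on surrogate measures says that both "correlate strongly with transplanted islet mass in patients who maintain euglycemia long-term". It is natural to ask why one should vary so much less than the other.

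That section also remarks that "these studies were performed in patients who were specially selected from those with optimal long-term beta cell function", which invites the suspicion that the 10 GPAIS patients were unusually alike.

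If day-90 AIRmax varied as much as AUC C-peptide, power for 33 mU/mL would be 27% rather than 80%. A null result read beside a stated 80% could then be taken as evidence against a 24% gain and count against an agent that works.

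**Working it through.** **The plan's own figure.** Inputs: 15 per arm, 80% power, SD 31, mean 137. Two-sided 0.05 per comparison is an assumption; it is the variant that returns the printed 1.06.

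- Two-sample t-test, 28 df, noncentral t: detectable effect = 1.060 SD.
- 1.06 × 31 = 32.9, rounded to 33 mU/mL; 33/137 = 24%.
- Power at 33/31: 80%.

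Every other detectable difference in the table also equals 1.06 × SD within rounding.

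**Relative variability (SD/mean).**

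| Measure | n | CV |
|---|---|---|
| AIRmax | 10 | 31/137 = 23% |
| AUC C-peptide | 39 | 139/295 = 47% |
| ACRglu | 36 | 8.3/9.8 = 85% |
| AIRglu | 33 | 153/169 = 91% |
| AUC glucose (not a secretion measure) | 39 | 3,579/16,037 = 22% |

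**Precision of SD 31.** Chi-square interval with 9 df (quantiles 19.02 and 2.70):

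- Lower limit: 31 × √(9/19.02) = 21.3. Upper limit: 31 × √(9/2.70) = 56.6.
- Detectable difference: 1.06 × 21.3 = 23 mU/mL (16% of 137) to 1.06 × 56.6 = 60 mU/mL (44%).
- Power for 33 mU/mL: 98% at SD 21.3; 34% at SD 56.6.

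The interval puts power on both sides of 80%.

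**Could chance produce the gap?** This is the probability that 10 patients show a CV of 23% or less, from 400,000 simulations under each distribution:

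- True CV 47%: about 1.6% (log-normal) or 1% (gamma).
- True CV 39%, the lower 95% limit for AUC C-peptide: about 4% to 5%.

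A 95% interval for the AIRmax CV by the noncentral t is 15% to 43%; that for AUC C-peptide is 39% to 61%. They overlap. Formal comparisons of this pair fall on either side of 0.05 (p = 0.03 from a log-scale variance ratio, 0.06 from an asymptotic CV test). AIRglu and ACRglu differ clearly from AIRmax, with p from 0.0005 to 0.02.

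**Should the CVs agree at all?** The definitions of the metabolic assessments describe different stimuli. AIRglu and ACRglu are baseline-subtracted areas over 10 minutes after one dextrose bolus. AUC C-peptide follows an oral meal. AIRmax is the response to arginine after at least 30 minutes with glucose held near 230 mg/dL, checked every 5 minutes. Two measures can both track islet mass and still have different relative spread.

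**Were the 10 selected?** The remark about specially selected patients concerns cited studies, and it covers AIRglu as well as AIRmax, so it cannot explain a low CV in AIRmax alone. The table places the 10 in the TPIAT population. With n = 10, mean 137 and SD 31, no value can lie below 137 − 31 × 9/√10 = 49. That bound only restates the SD and is not separate evidence of selection.

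**Effect of covariates.** The power figure takes no credit for the planned adjustment. If islet mass and BMI stratum explained an assumed 25% of variance, an SD of 36 would leave a residual SD of 36 × √0.75 = 31.2, and power would still be 80%.

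**The case for a change.** The strongest opposing case needs no comparison between tests. Sampling error in SD 31 alone allows power as low as 34%, so an unqualified 80% claims too much. The background also says that about 90% of recipients have functioning islets. Suppose 10% of trial patients had AIRmax near zero and the rest had mean 137 and SD 31. The overall SD would be √[0.9 × (31² + 137²) − (0.9 × 137)²] = 51, and power for 33 mU/mL about 41%. Covariates could not readily close a gap of that kind: at a CV of 47% they would have to explain 77% of the variance, while the background reports marked variation in diabetes outcomes at any given islet mass.

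The imprecision is real. A conditional sentence would read better: 33 mU/mL if the day-90 SD is 31, and about 23 to 60 mU/mL over the 95% interval for that SD. But a reader can already derive this from the printed n and SD, and power is given first in SD units, which hold at any SD. The 10% scenario is an assumption; the exclusion of patients with evidence of inadequate beta-cell mass works against it, by an unknown amount.

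The feared misuse of a null result is not in the plan. The abstract and the objectives use day-90 function together with mechanistic data to choose the more promising agent; neither makes significance a condition. For ranking, the design is less sensitive to the SD. With a true difference of 33 mU/mL, the better arm has the higher mean with probability Φ(33/(SD × √(2/15))), which is 99.8% at SD 31 and 92% at SD 64.5 (CV 47%).

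**Conclusion.** The concern does not call for a change. The calculation is correct under its printed inputs, and the small sample and late timing are disclosed. The low CV is a reason to treat 33 mU/mL as a rough figure; it does not establish that 31 is too small. The AIRmax data themselves support a detectable difference of about 23 to 60 mU/mL and power of about 98% to 34% for 33 mU/mL. This assumes 15 per arm, two-sided 0.05 per comparison, an approximately normal outcome, and that the SD seen beyond one year applies at day 90. CVs of 47% and above lie outside the interval for the AIRmax CV, and would matter only if the 10 patients were unrepresentative, which the documents do not show.

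Clearer wording would alter neither the sample size, the endpoint or the linear model, nor how an agent is chosen. For a pilot with openly stated inputs, relying on a small preliminary sample is a fair trade-off.
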